5.5.3. CCI

5.5.3.1. Definition

The proportion of participants with Section 5.4.3.1) will be assessed in the treatment period after the first 4 weeks to explore if the compound needs some time to develop effect. Only the subset of participants who remained in the treatment period beyond 4 weeks will be included. In other words, participants who exit the study by 4 weeks having reached their pre-randomization baseline seizure count will not be included.

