Participants who meet study entry criteria at the end of the prospective pretreatment baseline period will be randomized to JNJ-40411813 or placebo, CCI. The dosage(s) of concomitant AEDs should not be increased, and new concomitant AEDs should not be added to the treatment regimen. Central randomization will be implemented in this study. Participants will be randomly assigned to one of two treatment groups (JNJ-40411813 or Placebo) based on computer-generated randomization schedules prepared before the study by, or under the supervision of the sponsor. The randomization will be balanced by using randomly permuted blocks stratified by the prescribed baseline

Dosages of JNJ-40411813 in the first cohort will be CCI or placebo for or placebo for . Dosages of JNJ-40411813 in Cohort 2 will and Co be or placebo for or placebo for 7 days, dose increase or placebo on day 8) and . In the following for cohorts, the dose of JNJ-40411813 will be determined based on an ongoing assessment of tolerability and safety results from the previous cohort. The highest dose in following cohorts will for . The highest dose selected to be administered by induced participants will be expected not to exceed the 95th percentile of the plasma Cmax for JNJ-40411813, based on a population PK and/or PBPK model, after repeated administration of The minimum dose that might be considered in successive cohorts will be

Participants are encouraged to complete at least the first 4 weeks of treatment when there are no safety concerns. Participants who have exceeded their pre-randomization monthly seizure count at Week 4, or within any 4-week interval after Week 4 ("4-week sliding window approach") up to Week 12, will have the option to discontinue the study drug for lack of efficacy and to perform the end of study/early withdrawal visit, to continue double blind treatment, or to enter the OLE period. Participants who have not exceeded the pre-randomization seizure count will continue the double-blind treatment period through Week 12 and will have the option to perform the end of study visit or to enter the OLE period.

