4. POPULATIONS (ANALYSIS SETS) FOR ANALYSIS

For purposes of analysis, participants will be classified into the following analysis sets. For each analysis set described below, participants will be analyzed according to the planned study intervention irrespective of what they actually received.

Analysis Sets	Description				
Enrolled	All participants who sign the ICF.				
Randomized The randomized analysis set includes all participants who were randomized in					
Full Analysis Set	The full analysis set (FAS) includes all randomized participants assigned to receive				
(FAS)	study intervention and have both baseline and postbaseline seizure data. This definition				
	is the same as the ITT set.				
Full Analysis Set:	The FASOLE analysis set includes all FAS participants who received at least 1 dose of				
Open-Label	study intervention in the OLE phase.				
Extension					
(FASOLE)					
Compliance	The compliance analysis set (CAS) includes a subset of participants in the FAS who				
Analysis Set	were in compliance with their medication intake. In other words, exclude those who with				
(CAS)	<80% compliance for medication intake. Medication intake data will come from the dru				
	accountability data collected at monthly visits.				
"Modified" FAS	The modified FAS includes a subset of participants in the FAS who remained in the				
	treatment period beyond 4 weeks. In other words, participants who exit the study by 4				
	weeks having reached their pre-randomization baseline seizure count will not be				
	included.				
Safety (SAF)	The safety analysis set includes all randomized participants who received at least 1 dose				
C-f-t O	of JNJ-40411813 or placebo in the double-blind phase.				
Safety: Open-	The SAFOLE analysis set includes all randomized participants who received at least 1				
Label Extension dose of study intervention in the OLE phase. This analysis set is the same as the					
(SAFOLE)	FASOLE analysis set.				
PK Analysis Set	The PK analysis set (PKAS) included all randomized participants who have received at				
(PKAS)	least 1 dose of JNJ-40411813 and have at least 1 valid blood sample drawn for PK				
	analysis.				

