5.4.3. Responder rate

5.4.3.1. Definition

A secondary efficacy endpoint is the responder rate which is defined as a participant having at least a 50% reduction of the monthly seizure rate during the double-blind period. The percent reduction in the double-blind monthly seizure count is defined in Section 5.4.1.1. A participant is defined a responder (yes=1) if the percent reduction in the double-blind monthly seizure count is \geq 50%. Participants who do not meet such a criterion will be considered as non-responders and will be assigned a value of 0 (i.e. No). Participants who exit the study at Week 4 after reaching the baseline seizure count will be treated as non-responders in this analysis.

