5.5. Exploratory Endpoint(s) Analysis

All exploratory analyses will be based on the full analysis set apart from Section 5.5.3 (i.e. Seizure freedom and responder rate after the first 4 weeks) which will be based on the modified full analysis set and Section 5.5.4 (Efficacy data in the Open-Label Extension) which will be based on the FASOLE analysis set.

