5.5.3.2. Analysis Methods

For each cohort, the number and percentage of participants with CCI and, CCI and, CCI and and, CCI arte during the double-blind period after the first 4 weeks will be summarized by treatment group (JNJ-813 or Placebo) pooled over CCI and also treatment group CCI.

[figure not shown]

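### The after-Week-4 responder and seizure-freedom summary drops participants who failed and left by Week 4, so on its own it is not a randomised comparison and can mislead on onset of effect

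*SAP*

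**What the plan says.** SAP 5.5.3.1 gives the purpose of the analysis as "to explore if the compound needs some time to develop effect". SAP 5.5 names the endpoints and the set: "Seizure freedom and responder rate after the first 4 weeks) which will be based on the modified full analysis set". SAP 4 defines that set: "The modified FAS includes a subset of participants in the FAS who remained in the" treatment period past Week 4. It adds that those who leave by 4 "weeks having reached their pre-randomization baseline seizure count will not be" included. SAP 5.5.3.1 repeats the exclusion: "participants who exit the study by 4 weeks having reached their pre-randomization baseline seizure count will not be included". The visible method in 5.5.3.2 is a count and percentage by cohort and treatment group; I see no test or model.

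Leaving is optional. Under SAP 1.2, participants who have exceeded their count at Week 4 "will have the option to discontinue the study drug for lack of efficacy and to perform the end of study/early withdrawal visit". They may instead continue double-blind treatment or enter the open-label extension. An exit after reaching the count by Day 28 is classed as completing the double-blind period (protocol 7.2, SAP 5.1).

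The secondary responder analysis covers the whole double-blind period and keeps early exits in the FAS: "Participants who exit the study at Week 4 after reaching the baseline seizure count will be treated as non-responders in this analysis" (SAP 5.4.3.1).

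**The concern.** Reaching the baseline monthly count is the primary efficacy event. A set that removes people for reaching it by Week 4 and leaving is conditioned on outcome after randomisation. The remaining arms need not be comparable, and the late contrast can mix drug effect with selection.

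There is also an incentive to leave. Protocol 10.6.3 gives former placebo participants active drug in the open-label extension, so an early failure gains something by exiting. The documents do not say how many will.

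What is at stake is the answer to one question, whether the effect builds over time. That answer could inform the design of later studies. The trial's main efficacy conclusion is not at stake.

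**Working it through.** **The plan's own figures.** The plan gives no figure for this analysis. Its related figures are the primary power values: 99% and 83% (40:20, further reduction of 50% and 30%) and 94% (40:10, 50%). The documents name between-subject variability and overdispersion but give no values. Simulating daily overdispersed counts and testing time to baseline count at one-sided 0.05 gave:

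- 99.5%, 67.5% and 93.8% with a between-person SD of log response of 0.4;
- 100%, 81.9% and 98.9% with SD 0.25;
- 100%, 84.1% and 99.2% with SD 0.4 and an additive reading of the further reduction.

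Each stated value is reachable under some assumption, but no single setting gave all three. This is not evidence of an error. It means that the sizes below rest on assumed inputs.

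**Relation between the two displays.** In one arm, let *e* be the fraction excluded (reached the count by Week 4 and left), and let *p* be the proportion of all randomised who stay and respond in Weeks 5-12.

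- FAS rate, exits counted as non-responders = *p*
- Modified-FAS rate = *p* / (1 − *e*)

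The modified FAS therefore scales each arm up by 1/(1 − *e*). If *e* is equal in the arms, both rates rise by the same factor. If *e* is larger on placebo, placebo is scaled up more.

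**Assumed inputs.** Median baseline 10 seizures per 28 days (log-SD 0.9); 3 to 100 seizures in each 4-week half of baseline (protocol 5.1); placebo reduction 15% and drug a further 30% or 50% (protocol 9.1); response is at least a 50% reduction (SAP 5.4.3.1); response SD 0.4 or 0.7; 60,000 per arm.

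**Exclusion if every early failure leaves.** At SD 0.4: placebo about 39%, drug about 7% (constant 50%) or 18% (constant 30%). At SD 0.7: placebo 42%, drug 15% or 27%.

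**Worked case, effect in Weeks 1-4 only, SD 0.4.** Excluded: drug 0.074, placebo 0.386. FAS rates: 18.5% and 17.9%.

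- Drug: 18.5 / 0.926 = 20.0%
- Placebo: 17.9 / 0.614 = 29.2%

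The difference is about −9 points (−9.3 before rounding). The true late difference is zero by construction.

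**Weeks 5-12 responder difference, drug minus placebo, in points**

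| Effect | SD | Truth, had all stayed | Modified FAS, all leave | FAS, all leave | Modified FAS, half leave |
|---|---|---|---|---|---|
| Constant 50% | 0.4 | 45.8 | 40.0 | 45.8 | 43.9 |
| Constant 50% | 0.7 | 33.1 | 24.6 | 33.1 | 30.8 |
| Constant 30% | 0.7 | 16.8 | 13.3 | 16.6 | 16.3 |
| Weeks 1-4 only, 50% | 0.4 | −0.6 | −9.3 | +0.6 | −3.7 |
| Weeks 1-4 only, 50% | 0.7 | −0.3 | −13.8 | +0.7 | −4.8 |
| Week 5 on only, 30% | 0.4 | 21.5 | 28.7 | 17.6 | 24.3 |
| Week 5 on only, 30% | 0.7 | 15.8 | 23.0 | 13.1 | 18.4 |
| None | 0.7 | 0.1 | 0.0 | 0.0 | 0.1 |

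The small non-zero truths in the Weeks 1-4 and null rows are simulation noise. At SD 0.4 the constant 30% effect gave 19.7 in the modified FAS against 22.1.

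With an inert drug the arms agree, but if all early failures leave, the responder rate in both rises from about 19% to 28% (SD 0.4) or from 27% to 45% (SD 0.7). A separate simulation with a 40% effect showed the same pattern: −7 to −10 points for an early-only effect, and 2 to 8 points of understatement for a constant one.

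**Numbers left.** If all early failures leave, about 12 of 20 placebo participants remain in Cohort 1, or 6 of 10 in a later cohort. With 12 remaining at 28%, the standard error of that percentage is √(0.28 × 0.72 / 12) = 0.13, or 13 points.

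**The case against.** The other side has several good points.

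- **Low stakes.** The analysis is exploratory and descriptive, with no visible test or decision rule. The primary and secondary efficacy analyses use the FAS.
- **Balance under the hypothesis being explored.** Arm imbalance needs a drug effect in Weeks 1-4. If the effect is purely late, early failure is equally likely in both arms, and the gap between 28.7 and 21.5 reflects a different population (early survivors), not confounding between arms.
- **Optional exit and noise.** With half leaving, the distortions are below 5 points, whereas one participant is 5 points of a placebo arm of 20 and 10 points of an arm of 10.
- **The FAS version is also imperfect.** It carries failure in Weeks 1-4 into a question about Weeks 5-12. For a purely late effect it gave 17.6 against 21.5, and 13.1 against 15.8. Other settings put the shortfall as high as about 13 points.
- **Redaction.** Parts of 5.5.3 are blacked out, so a caveat there cannot be ruled out.

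All of this stands, and it makes the point minor. It does not remove it, because the reader of the planned table will not know which effect pattern holds, and that table alone cannot separate them.

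Two stronger readings are tempting. A reader might infer that 5.5.3 contradicts 5.4.3.1. It does not: 5.4.3.1 concerns the whole double-blind period, in which early exits have observed seizure data, while 5.5.3 concerns the period after they have left. A reader might also infer that the size of the exclusion will go unreported. SAP Appendix 3 already has the number in each analysis set summarised by treatment group, so FAS minus modified FAS essentially gives it.

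**Conclusion.** The point holds as a minor one. The modified FAS is selected on an efficacy failure after randomisation, and the direction of the resulting error depends on when the drug acts:

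- Early or constant effect, with many exits: the late contrast is understated or falsely favours placebo.
- Purely late effect: exclusion is balanced, but the figure applies to early survivors and exceeds the all-randomised difference.
- No effect: no between-arm bias, but inflated levels in both arms could be read as a delayed gain.

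The sizes in the table rest on assumed baseline, overdispersion and response variance, and on an exit rate that the documents do not give. They cover responder rate only; the selection mechanism is the same for seizure freedom. The mechanism follows from the SAP text. A reader might infer that the exclusion always works against the drug, or that it threatens the main efficacy results; the documents support neither.

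**What to change.** Keep the planned modified-FAS table and label it a non-randomised subset. Beside it, show the same Weeks 5-12 summary on the FAS, with participants who exited by Week 4 after reaching their count shown as non-responders and not seizure-free. Footnote that the two are to be read together and that the FAS version is conservative for a purely late effect.

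The footnote should also say how participants who left by Week 4 for other reasons are handled. The first sentence of the SAP 4 definition would leave them out, while its restatement names only those who reached their count.

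The cost is one extra table from data already collected. Replacing the planned table is not warranted, since each version answers part of the onset question.

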5.5.3.2. Analysis Methods

For each cohort, the number and percentage of participants with CCI and, CCI and, CCI and and, CCI arte during the double-blind period after the first 4 weeks will be summarized by treatment group (JNJ-813 or Placebo) pooled over CCI and also treatment group CCI.

[figure not shown]
5.5.4. Analysis of Efficacy data in the Open-Label Extension

Efficacy assessments during the open-label extension phase include percent reduction in seizure frequency, the percent of participants with seizure freedom and the participant responder rate.

The percent reduction in the OLE monthly seizure count is defined as 100*(Baseline monthly seizure count - OLE monthly seizure count)/(Baseline monthly seizure count). The OLE monthly seizure count is defined as the total number of observable focal onset seizures occurring during the OLE period, multiplied by 28/X_{OLE}, where X_{OLE} is the number of days comprising the OLE.

Descriptive statistics (N, mean, SD, median, 25th percentile and 75th percentile) of the percent reduction in the OLE monthly seizure rate will be presented. The number and percentage of participants with seizure freedom at the end of the OLE period will be summarized. The number and percentage of participants who achieve a response during the OLE period will be presented.

The analyses will be performed for the FASOLE analysis set for the open-label phase.

Plots of the mean (±SE) percent reduction in seizure count over time spanning the double-blind and open-label phase will also be presented for the observed cases by the double-blind treatment group (in the form of an intervention sequence) pooled over and also treatment group by CCI If the nature of the outcome is nonparametric then box-plots for the percent reduction in seizure count will be presented instead.

5.6. (Other) Safety Analyses

All safety analyses will be based on the safety (SAF and SAFOLE) analysis sets based on actual intervention received, unless otherwise specified.

For all continuous safety variables, descriptive statistics by intervention group will include the N, mean, standard deviation, median, minimum, and maximum. Categorical variables will be summarized by intervention group using frequency counts and percentages.

Analysis of safety data in the open-label phase: All open-label safety data will be summarized by the intervention received in the double-blind phase (in the form of an intervention sequence), and overall.

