# 10. ADDENDUM FOR OPEN-LABEL EXTENSION (OLE) PERIODa

#### 10.1. Rationale

This is an OLE period to investigate the long-term safety and efficacy of JNJ-40411813 in subjects who completed their participation in the double-blind study period. This study period will allow study participants to continue treatment and evaluate long-term safety and efficacy of JNJ-40411813 in epilepsy. Also study participants that have been treated with placebo may be included in the OLE period.

Because epilepsy is a chronic condition, often requiring treatment for years, long-term data should be generated by conducting OLE studies in order to assess for maintenance of efficacy and safety. Treatment retention rate is recommended as a global indicator of clinical effectiveness. A one-year study duration is considered the minimum (EMA 2018).

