#### 10.8.3. Efficacy Assessments in the OLE period

#### 10.8.3.1. Seizure count

The key efficacy evaluation is seizure count; #seizures per 28 days calculated as (28/the number of days between visits)\*(seizures counted between the visits).

The participant and/or caregiver will be provided access to an (electronic) diary to record seizures. The e-diary will be an app downloaded on the smartphone owned by the participant. Only if the participant and/or caregiver do not own a smartphone, a smartphone programmed for the study will be provided.

Participants must be compliant with the recording of information in the e-diary throughout the study. Seizures that will be entered during baseline and throughout the study include focal aware seizures with and without motor signs, focal impaired awareness seizures and focal to bilateral tonic-clonic seizures. Myoclonic, or other generalized seizures will not be entered.

[figure not shown]

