6.2. Appendix 2 Changes to Protocol-Planned Analyses

There have been no changes to protocol-planned analyses.

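### SAP 5.5.4 tabulates OLE percent reduction and response only from one whole-OLE seizure rate, while Protocol 10.8.3.1 defines the rate per between-visit interval, so the tables cannot separate maintained from lost effect

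*SAP*

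**What the plan says.** Protocol 10.8.3.1 names the seizure count per 28 days as the key OLE efficacy evaluation, "calculated as (28/the number of days between visits)\*(seizures counted between the visits". That gives one value for each interval between visits. Protocol 10.1 gives the reason for the extension: "long-term data should be generated by conducting OLE studies in order to assess for maintenance of efficacy and safety". Long-term efficacy is part of the primary OLE objective in Protocol 10.3, and Protocol 10.4.2 sets the duration at up to 2 years.

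SAP 5.5.4 defines a different quantity. "The OLE monthly seizure count is defined as the total number of observable focal onset seizures occurring during the OLE period". This total is then put on a 28-day scale using X_OLE, the participant's OLE length in days, so each participant has a single value. Descriptive statistics of the "percent reduction in the OLE monthly seizure rate will be presented", together with the number and percentage with a response during the OLE. Neither summary is broken down by visit or interval.

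The same section plans a display over time. Mean (±SE) plots of "percent reduction in seizure count over time spanning the double-blind and open-label phase will also be presented for the observed cases", by intervention sequence. "If the nature of the outcome is nonparametric then box-plots for the percent reduction in seizure count will be presented instead".

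SAP Table 2 lists windows for the individual OLE visits for laboratory tests, examinations, C-SSRS and vital signs. For e-diary seizure counts it has a single OLE row, from the end of the double-blind period to the end of the OLE. SAP Appendix 2 states: "There have been no changes to protocol-planned analyses".

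**The concern.** Maintenance of efficacy is a question about the time course. A participant's whole-OLE rate is a time-weighted average, so an early benefit that is later lost can give the same number as a stable, smaller benefit. Responder status then turns that average into one yes or no. The average also puts a participant who stayed one month and one who stayed two years into the same table on the same footing.

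The OLE has no control arm and no hypothesis test, so these descriptive tables are the main numerical evidence on whether the effect lasts. As specified, they do not report the measure the protocol names, and they cannot show the pattern the extension was added to look for.

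**Working it through.** The plan gives no OLE sample size, power or target figure, so there is nothing of its own to reproduce. The check applies both definitions to the same hypothetical participants.

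**Inputs from the documents**
- Target visit days (SAP Table 2; Protocol 10.10, footnote k): 31, 62, 93, then every 90 days: 183, 273, 363, 453, 543, 633, 723. OLE7 falls on day 363, OLE9 on day 543 and OLE11 on day 723.
- This gives ten intervals: three of 31 days and seven of 90 days, and 93 + 630 = 723 days. OLE1 is taken as the start of the count.
- Response is at least a 50% reduction (SAP 5.4.3.1). That rule is written for the double-blind period and is assumed to carry over to the OLE.

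**Assumption:** the reduction profiles below are illustrative. They are not trial data or forecasts.

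**Formulas.** Let B be the baseline count per 28 days, and let r_i be the percent reduction in interval i, which lasts d_i days.
- Protocol, per interval: the rate is B(1 − r_i/100), so the reported reduction is r_i.
- SAP, whole OLE: total seizures = Σ (B/28)(1 − r_i/100) d_i. Multiplying by 28/X_OLE and comparing with B gives a percent reduction of Σ r_i d_i / Σ d_i. B cancels.

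| Assumed profile | SAP calculation | SAP result | SAP status | Protocol intervals |
|---|---|---|---|---|
| Steady 50% | 50 throughout | 50.0% | Responder | 50% in all ten |
| 70% to OLE7, then 30% | (70×363 + 30×360)/723 = 36,210/723 | 50.1% | Responder | 70% in six, then 30% in four |
| 80% to OLE9, then 0% | (80×543 + 0×180)/723 = 43,440/723 | 60.1% | Responder | 80% in eight, then 0% in two |
| 80% falling linearly to 20% | (220×31 + 280×90)/723 = 32,020/723 | 44.3% | Non-responder | First five at or above 50%, last five below |
| 60% to OLE7, then 0% | (60×363 + 0×360)/723 = 21,780/723 | 30.1% | Non-responder | 60% in six, then 0% in four |

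In the fourth row, 220 is the sum of the reductions over the three 31-day intervals (80, 73.3, 66.7). The figure 280 is the sum over the seven 90-day intervals (60 down to 20).

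Rows 1 and 2 cannot be told apart in the SAP tables, although one participant has kept the effect and the other has been below the response threshold for the last four intervals. Row 3 ends with no effect at all and has the highest score of the five. The per-interval calculation separates all of them.

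**The case against.** A reader might infer that loss of effect disappears from the OLE efficacy results altogether. The documents do not support that. SAP 5.5.4 plans percent-reduction plots over time, with box-plots as the fallback, and plots drawn by visit interval would show every decline in the table above. What remains is narrower. No interval is stated for the plots, and the only OLE rate the SAP defines is the whole-period one. The display is graphical only. It uses observed cases, so it can look better as participants who lose benefit leave, which Protocol 10.4.1 allows. It does not cover responders.

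A reader might also infer that the statement in SAP Appendix 2 is wrong. That is arguable. The per-interval formula sits among the efficacy assessments. Protocol 10.9.2 asks only for descriptive statistics and graphs, and leaves the OLE analysis to the SAP. The protocol prescribes no by-interval table that the SAP could be said to have dropped.

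Three further points count against a strong reading:
- Protocol 10.1 also recommends retention as a global indicator of effectiveness, and SAP 5.6.1 tabulates OLE treatment duration in 4-week bands to week 104 and beyond. This shows how long people stayed, but it is not linked to their seizure outcome.
- Participants whose benefit has gone may withdraw, so a long tail at zero effect may be uncommon.
- By-interval rates among those who remain will mix drug effect, selection and the changes in concomitant AEDs permitted by Protocol 10.4.1.

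The last two points limit how the interval results can be read. They apply to the whole-OLE average as well, where they are harder to see.

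**Conclusion.** The point holds for the tables. SAP 5.5.4 reports percent reduction and response from one whole-OLE rate, the protocol's key measure is a rate per between-visit interval, and the SAP sets no OLE intervals for seizure counts. Under the assumed profiles, a fall from 70% to 30% after OLE7 reads the same as a steady 50% (50.1% against 50.0%, both responders). A complete loss after OLE9 still reads 60.1% and responder.

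The size in practice depends on how many participants lose effect and stay in the OLE, which the documents cannot tell us. The examples show what the tables can miss, not what the trial will find. The planned plot is a partial remedy for percent reduction and none for the responder rate. The OLE is descriptive and SAP 5.5 places this analysis among the exploratory ones, so no alpha, power or double-blind conclusion is at risk. It is a modest, inexpensive improvement that answers the extension's own question.

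**What to change.** In SAP 5.5.4:
1. Compute seizures per 28 days for each of the ten between-visit intervals (OLE1–2 to OLE10–11), as in Protocol 10.8.3.1, and add these intervals to the seizure-count row of Table 2.
2. Tabulate percent reduction (N, median, quartiles) and responder rate by interval and intervention sequence, with the number of participants still in the OLE at each interval.
3. State that the plots over time use the same intervals.
4. Keep the whole-OLE average as a supplementary summary.
5. Add a sentence saying that by-interval results describe those remaining and reflect dropout and permitted AED changes.

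If the sponsor prefers to keep only the whole-OLE tables, the difference from Protocol 10.8.3.1 is better noted in Appendix 2 than left unstated.

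The cost is SAP wording and one more descriptive table. The diary entries and visit dates are already collected under Protocol 10.10, and no visit or procedure changes.
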